**Effects of Bright Light on Co-occurring Cancer-related Symptoms
in Breast Cancer Survivors**

NCT03304587

PI: [name]

Study Procedures

May 1, 2022

Recruitment

- 1) The tumor registry at the Sparrow Hospital will be utilized for the study recruitment. The tumor registry will provide the principal investigator with a list of names and contact information (address, phone number, and/or email) of those individuals who may be eligible for the study. An invitation letter and the study flyers will be mailed to the potential candidates. Up to 2 follow-up reminders will be mailed 2-3 and 4-5 weeks after the initial mail. Those who are interested in participation can either call or email the principal investigator. The initial phone conversation will start with the principal investigator or a research assistant introducing herself/himself. Only when the person agrees, the principal investigator or a research assistant will briefly discuss the study and then schedule the visit for recruitment/consent.
- 2) ResearchMatch.org will be utilized as a recruitment tool for this study. Recruitment message from ResearchMatch will be sent to the matched volunteers. The individuals can then let the ResearchMatch team know whether they are interested or not. The ResearchMatch team will then release the contact information of those who have expressed their interest to the principal investigator. The initial phone conversation will start with the principal investigator or a research assistant introducing herself/himself. Only when the person agrees, the principal investigator or a research assistant will briefly discuss the study with the persons and then schedule the visit for consent.
- 3) Recruitment materials (flyers) will be placed at public areas (e.g. college of nursing building etc.) and at the clinics (e.g. waiting area). Those who are interested in participation can either call or email the principal investigator. The initial phone conversation will start with the principal investigator or a research assistant introducing herself/himself. Only when the person agrees, the principal investigator or a research assistant will briefly discuss the study with the persons and then schedule the visit for recruitment/consent.

Procedures

If the candidate agrees to be approached, the investigator/research assistant will contact the candidate over the telephone. The topic and the purposes of the study will be introduced. If the candidate is interested, the investigator/research assistant will schedule the visit for recruitment/consent. (Script is followed)

The recruitment/consent visit will be either on the day of the individual's convenience. The investigator/research assistant will provide explanation of the screening, the study procedures involved, the time commitment, and the purpose of written consent. Also, the candidates will be told that phone calls will be made during the study period. Potential subjects will be instructed to read the consent forms carefully. Any questions will be answered before signing. Before written consent is obtained, no personal information will be revealed or recorded. (Pink folder)

After giving informed consent, candidates will first complete the demographic information and 4 self-administered screening tools including the Horne-Ostberg Morningness-Eveningness Questionnaire (MEQ), the International Statistical Classification of Diseases and Related Health Problems (10th revision) (ICD-10) criteria for cancer-related fatigue, Pittsburgh Sleep Quality Index (PSQI), and the Center for Epidemiological Studies Depression Scale (CES-D). A research staff will instruct the participant and administer the Montreal Cognitive Assessment (MoCA) with paper and pencil. After that, candidates will then be individually screened/interviewed for the exclusion criteria (scoring criteria provided). Those who met the study criteria will be scheduled of the study activities (Blue folder).

Participants will be enrolled in the study for approximately 3 weeks. Each participant will make 3 overnight visits to the sleep laboratory. The research protocol consists of a pre-study adaptation night, baseline data collection, 14-day treatment phase, and post-treatment data collection. Night-time Sleep patterns and overnight core body temperature will be monitored in a sleep laboratory before and after the bright light intervention.

	Pre-Study	Baseline		Treatment	Post-Treatment	
Study Day	(prior baseline)	D1	D2	(14 consecutive days)	D1	D2
Bright light protocol				X (daily)		
Polysomnography (overnight only)	Adaptation night	X	End		X	End
Core body temperature (overnight only)	Adaptation night	X	End		X	End
Self-reported measurement* & cognition assessment		X			X	
Daily log		X	X	X (daily)	X	X

Pre-study adaptation night: To facilitate adaptation to sleep study procedures and a new sleep environment, the participants will report to the sleep laboratory around 8 pm on a convenient weekday. After checking in to the sleep laboratory, the research staff will provide instruction for daily log. A study schedule will be provided to the study participant (completed by a research staff). The sleep lab staff will give a tour to sleep lab. Before going to bed, the person will then be connected to the polysomnography (PSG) recording and undergo continuous PSG for one night. The recorded PSG data during the adaptation night will not be analyzed as per standard sleep research methodology.

The participants will be instructed to complete the 8 self-administered instruments, including PROMIS-Sleep Disturbance, PSQI, PROMIS-Fatigue, PROMIS-depression, CES-D, EORTC

QLQ-C30, PROMIS-Physical Function, and PSS on the day of baseline data collection (blue folder). They will be asked to return the completed instruments on their next sleep lab visit.

Starting from the adaptation night and throughout the study, the participants will complete the daily log each morning and before going to bed to record sleep/wake activities, naptimes, and levels of fatigue throughout the day.

Baseline data collection: Within a week (prefer next day), the participants will return to the sleep laboratory around 7 pm. After checking in the sleep lab), the participants will complete the NIH Toolbox Cognition Battery via iPad Air (administered by the research staff).

The participants will be connected to the PSG recording before going to bed and undergo overnight PSG monitoring. The recording for the PSG analysis will start at the time of lights out and will end at the time of final awakening in the morning (when the individual is out of bed). With the assistant from a research staff, the participant will be instructed to self-insert the thermistor just before going to bed and will remove (by herself) thermistor after final awakening in the morning. Core temperature readings will be continuously monitored and recorded every 5 minutes during the all-night sleep studies. The data at 5 minute intervals starting with lights out will be used for analysis.

(sleep lab instruction provided, in pink folder) The participants will be asked to refrain from consuming alcohol, using tobacco, and taking over-the-counter sleep or allergy medication during the 12-hour period before checking in to the sleep laboratory and throughout the laboratory session. Snacks (provide to participants at each sleep lab visit) will be available and breakfasts will be provided. The participants are encouraged to bring their personal items, engage in daily activities, e.g., watching TV, reading, etc., and maintain their bedtime ritual during their stay in the sleep laboratory.

Treatment phase: The treatment phase will start on the next day after the completion of baseline data collection. A light visor cap (Physician Engineered Products, Fryeburg, ME) and individualized instruction will be provided upon checking out of the sleep laboratory. A research staff meets with the study participant before checking out. The participants will be instructed to wear the light visor cap with the light on for 30 minutes either within 30 minutes of waking or between 1900-2000 hours for 14 consecutive days. A multiple-alarm watch will be provided (optional). Alarms will be set for on and off times by a research staff. To ensure participant comprehension and ability to perform the personalized light treatment at home, the individual will be asked to demonstrate knowledge of (by verbalizing the time of the day, frequency, and duration of prescribed light treatment) and ability to use (by demonstrating) the light visor cap.

In addition, provide instruction about light meter use. On 2 randomly selected days, one weekday and one weekend day, the subjects will wear a light meter during wake time, starting from rising in the morning and ending at bedtime in the evening. To enhance adherence to the use of the light meter, participants will receive a phone reminder the day before.

Throughout the 14-day treatment phase, the participants will continue completing the daily log each morning and before going to bed. In addition, they will be instructed to record the time of

the beginning and the end of each light treatment on the daily log. Participants will receive a daily phone call from a research staff member for the first 1-3 days and then weekly phone calls for the rest of the treatment phase.

The participants will be instructed to complete the 8 self-administered instruments, including PROMIS-Sleep Disturbance, PSQI, PROMIS-Fatigue, PROMIS-depression, CES-D, EORTC QLQ-C30, PROMIS-Physical Function, and PSS on the day of posttest data collection. They will be asked to return the completed instruments on their sleep lab visit.

Post-treatment data collection: The post-treatment data collection will start on the next day after completion of the 14-day intervention protocol. Following the same protocol described in baseline data collection, the participants will report to the sleep laboratory 7 pm and then complete the MoCA and the NIH Toolbox Cognition Battery, administered by a research staff.

Before going to bed, the participants will be connected to the PSG recording at their regular bedtime hours and undergo overnight PSG monitoring. With the assistant from a research staff, the participant will self-insert the thermistor just before going to bed and will remove thermistor after final awakening in the morning. The PSG and core temperature recordings for the analysis will start at the time of lights out and will end after final awakening in the morning. During the post-treatment data collection, the participants will complete the daily log before going to bed and the following morning.

Before checking out of the sleep laboratory, the participant will return the daily log. All participants will receive an exit interview before checking out the sleep lab or within 3 days regarding issues or difficulties encountered during the study and complete a list of rating scales measuring levels of burden for study activities.

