**Effects of Bright Light on Co-occurring Cancer-related Symptoms
in Breast Cancer Survivors**

NCT03304587

PI: [name]

Statistical Analysis Plan

May 1, 2022

Statistical Analysis Plan

The data analysis of **Aim 1** will be descriptive in nature. To assess the feasibility of the proposed study protocol, the numbers of subjects contacted and screened, the proportion of eligible subjects from those contacted, the proportion of those successfully recruited from the pool of eligible subjects, the proportion retained of those recruited, completeness of the data collected, ease of using each measure, and adverse effects (if there are any) will be described using summary statistics. Adherence to treatment will be assessed by measuring timing of visor cap usage. Adherence to outcome reporting will be evaluated by estimating completion rates of scheduled PSG recordings, core body temperature measures, and self-report forms at both time periods. The proportion and the reason for missing data on each outcome will also be assessed.

The objective of **Aim 2** is to assess the effects of bright light on the 4 symptoms (sleep disturbance, fatigue, depression, cognitive dysfunction) and quality of life. Nocturnal sleep patterns will be measured objectively and subjectively. Objective sleep patterns will be monitored in a sleep laboratory by all-night PSG before and after the light intervention. The endpoints for sleep patterns (the sleep continuity measures include sleep onset latency, arousals, wake after sleep onset, and sleep efficiency) will be derived from scoring the PSG record by a polysomnographer blind to intervention assignment. Subjective endpoints for sleep patterns (sleep onset latency, sleep disturbance, and sleep efficiency) will be self-reported by participants before and after the light intervention. For each endpoint, the between-group difference will be compared using two-way ANOVA for repeated measurement data and to account for potential correlation among multiple measurements taken from the same individual. Important covariates such as ambient light and the level of stress (as measured by PSS) will be adjusted if necessary. Fatigue, depression, cognition, and quality of life will be subjectively and objectively assessed before and after the light intervention. Between-group differences in those subjective measurements will be compared using two-way ANOVA.

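### Adverse effects are an Aim 1 outcome, but the only described enquiry about problems is a general exit interview 15 to 18 days after the first treatment day

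*Protocol*

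**What the plan says.** The SAP, under Aim 1, closes its list of feasibility items with "and adverse effects (if there are any) will be described using summary statistics". The aim as a whole is non-inferential: "The data analysis of Aim 1 will be descriptive in nature".

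The Protocol describes these points at which an effect could come to light:

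- **Daily log.** Under Pre-study adaptation night, its purpose is "to record sleep/wake activities, naptimes, and levels of fatigue throughout the day". Under Treatment phase it continues twice a day ("Throughout the 14-day treatment phase, the participants will continue completing the daily log each morning and before going to bed"), and participants add "the beginning and the end of each light treatment on the daily log".
- **Staff calls.** Under Treatment phase: "Participants will receive a daily phone call from a research staff member for the first 1-3 days and then weekly phone calls". What is asked is not stated.
- **Light-meter reminders.** Also under Treatment phase, a phone reminder comes the day before light-meter use, which takes place on two days. Its stated purpose is adherence to the meter.
- **Exit interview.** Under Post-treatment data collection: "All participants will receive an exit interview before checking out the sleep lab or within 3 days". Its subject is problems met in the study in general, and it is accompanied by ratings of how burdensome each study activity was.

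**The concern.** A feasibility aim should show, among other things, how well participants tolerate the intervention. The SAP promises a summary of adverse effects, yet no definition, standard question, collection time or data source stands behind it. The one record kept every day, the log, has no described place for an effect. The one contact whose described subject would reach unwanted effects comes after treatment is over.

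Two things are at stake. Effects that are mild, brief or confined to the first days are the easiest to forget by the exit interview, so the summary may understate them. The reason for a shortened or skipped light session may also go unrecorded, which weakens the Aim 1 adherence summary as well as the adverse-effect one.

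**Working it through.** **Inputs.** Treatment phase: 14 consecutive days (Protocol, Treatment phase). Post-treatment D1 is the day after the last treatment day, and check-out is on D2 (Protocol, schedule table and Post-treatment data collection). Exit interview: at check-out or within 3 days. Log: two entries a day. The documents give no adverse-effect rate, definition or sample size, so there is no plan figure to reproduce.

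**Step 1: described content, side by side.**

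| Contact | When | Described content | Adverse effects named? |
|---|---|---|---|
| Daily log | Twice daily | Sleep/wake, naps, fatigue, light start and end | No |
| Staff calls | Daily at first, then weekly | None stated | No |
| Light-meter reminders | Day before each of 2 days | Reminder to wear the meter | No |
| Exit interview | Check-out or within 3 days | Problems in general | No, but could cover them |

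**Step 2: recall interval.** Number the treatment days 1 to 14. Post-treatment D1 is then day 15 and D2 is day 16. For an effect on treatment day *t*, the interval to the exit interview is 16 − *t* days at check-out, and 16 + 3 − *t* = 19 − *t* days at the latest.

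- *t* = 1: 16 − 1 = 15 days, up to 19 − 1 = 18 days.
- *t* = 7: 16 − 7 = 9 days, up to 19 − 7 = 12 days.
- *t* = 14: 16 − 14 = 2 days, up to 19 − 14 = 5 days.

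The earliest effects therefore have the longest recall. These intervals apply to any effect not raised at an earlier contact.

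**Step 3: what the log could capture.** Over treatment the log is completed 14 × 2 = 28 times, 14 of them before bed. Each day's light session, whether after waking or in the early evening, should precede the bedtime entry, so that entry could capture an effect on the same day. As described, the log's start and end times would show that a session was short or missing, but not why.

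**The case against.** The strongest defence is that Aim 1 is descriptive, with no test or threshold attached to adverse effects, and that every participant does have an exit interview. The log form, any call script and the interview form are not in the documents, so a line that is not described may still exist. Staff also speak to participants during treatment and see them in person on the post-treatment evening, so an effect on day 1 need not wait 15 days to be heard. All of this is fair and limits the weight of the point. It does not supply the missing question or the missing source for a listed outcome.

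A reader might go further and infer that the count depends on how often a participant was called, and hence that a comparison between groups is biased. The call rule does permit different totals. One daily call plus a weekly call on day 8 makes 1 + 1 = 2; three daily calls plus a weekly call on day 10 make 3 + 1 = 4. With a weekly call in each of the two weeks the totals are 1 + 2 = 3 and 3 + 2 = 5. The documents do not support the inference, for four reasons:

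- They do not say that the calls ask about adverse effects or feed the count.
- The range of days permits variation but does not state it. It can be applied alike to everyone, and nothing links it to group.
- The SAP sets out between-group comparisons for Aims 2 and 3. It states none for adverse effects.
- A two-fold ratio leaves out the light-meter reminders. If these count as contacts on the same footing, with one for each of the two days, 2 versus 4 becomes 4 versus 6 (1.5-fold) and 3 versus 5 becomes 5 versus 7 (1.4-fold).

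Even if calls did ask, the exit interview would absorb part of any difference. Suppose each of *k* calls independently detects an effect with chance *p*, and the interview with chance *q*. The chance of capture is then 1 − (1 − *p*)^*k* × (1 − *q*). With *p* = 0.3 assumed, 2 versus 4 calls gives 51% versus 76% at *q* = 0, but 90% versus 95% at *q* = 0.8. Both *p* and *q* are assumptions, so this illustrates the mechanism and does not estimate its size in this trial.

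**Conclusion.** The point holds as a gap in data capture. An outcome listed in the SAP has no stated definition, question or source. None of the 28 log entries due during treatment is described as having a place for an unwanted effect. The only enquiry about problems whose content is described comes 15 to 18 days after the first treatment day and 2 to 5 days after the last. Brief or early effects, and their part in shortened or skipped sessions, can be missed or misrecalled.

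The number that would be lost cannot be estimated from the documents. The conclusion assumes that the log, calls and interview contain no more than the Protocol describes, and that the post-treatment visit falls on the day stated. It does not extend to bias from call frequency or to a biased group comparison. This is a modest weakness, worth correcting because correction is cheap.

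**What to change.** 1. **Protocol, Treatment phase.** Add one line to the existing evening log entry: any unwanted effect today (yes/no), what it was, and whether the light session was shortened or skipped because of it.
2. **Protocol, Treatment phase and Post-treatment data collection.** Ask the same question at each staff call and at the exit interview. Set one fixed call schedule for all participants, within the range the Protocol already allows.
3. **SAP, Aim 1.** State what counts as an adverse effect. Summarise participants with at least one effect recorded in the log or at a call, and show effects first reported at the exit interview as a supplement. Report the number of contacts made.

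**Cost.** One extra line in each of 14 evening entries per participant, one scripted question per call, and a few sentences in the SAP. Fixing the schedule within the existing range adds at most 3 − 1 = 2 daily calls for any participant. Prompting will give a somewhat higher count than spontaneous report, and the write-up should say that the effects were prompted.

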**Effects of Bright Light on Co-occurring Cancer-related Symptoms
in Breast Cancer Survivors**

NCT03304587

PI: [name]

Statistical Analysis Plan

May 1, 2022

Statistical Analysis Plan

The data analysis of **Aim 1** will be descriptive in nature. To assess the feasibility of the proposed study protocol, the numbers of subjects contacted and screened, the proportion of eligible subjects from those contacted, the proportion of those successfully recruited from the pool of eligible subjects, the proportion retained of those recruited, completeness of the data collected, ease of using each measure, and adverse effects (if there are any) will be described using summary statistics. Adherence to treatment will be assessed by measuring timing of visor cap usage. Adherence to outcome reporting will be evaluated by estimating completion rates of scheduled PSG recordings, core body temperature measures, and self-report forms at both time periods. The proportion and the reason for missing data on each outcome will also be assessed.

The objective of **Aim 2** is to assess the effects of bright light on the 4 symptoms (sleep disturbance, fatigue, depression, cognitive dysfunction) and quality of life. Nocturnal sleep patterns will be measured objectively and subjectively. Objective sleep patterns will be monitored in a sleep laboratory by all-night PSG before and after the light intervention. The endpoints for sleep patterns (the sleep continuity measures include sleep onset latency, arousals, wake after sleep onset, and sleep efficiency) will be derived from scoring the PSG record by a polysomnographer blind to intervention assignment. Subjective endpoints for sleep patterns (sleep onset latency, sleep disturbance, and sleep efficiency) will be self-reported by participants before and after the light intervention. For each endpoint, the between-group difference will be compared using two-way ANOVA for repeated measurement data and to account for potential correlation among multiple measurements taken from the same individual. Important covariates such as ambient light and the level of stress (as measured by PSS) will be adjusted if necessary. Fatigue, depression, cognition, and quality of life will be subjectively and objectively assessed before and after the light intervention. Between-group differences in those subjective measurements will be compared using two-way ANOVA.

The objective of **Aim 3** is to assess the effects of bright light on circadian rhythms. Circadian rhythm will be measured by nocturnal core body temperature before and after the light intervention. The phase shift of the nocturnal core body temperature will be calculated by the timing of the peak and trough of the temperature curve. To take full advantage of the availability of intensive data from continuous sleep-time core body temperature measurement, the difference in circadian rhythms between groups will also be compared using functional data analysis (FDA), a collection of emerging techniques about the analysis of information on curves or functions. Unlike the conventional methods such as ANOVA that only focus on the differences at a few fixed time points, FDA provides information about curves, surfaces, or anything else varying over a continuum. Specifically, after a proper registration or alignment of the temperature curves from each individual, FDA will allow us not only to compare the overall circadian rhythms between groups, but also correlate the curves with other measured data such as symptom scores from Aim 2. Such a curve-based analysis will allow us to compare not only the magnitude (peak and trough) but also the shift in the circadian cycle.

Mediation analysis will also be performed to better understand the possible mechanism of bright light intervention on the 4 symptoms. Specifically, functional principal component analysis (FPCA) will first be applied to core body temperature during pre- and post-treatment periods separately to identify distinct patterns of circadian rhythms. The causal-step approach outlined in the classic work of mediation analysis will then be used to estimate the direct and indirect treatment effects and to quantify the potential mediating effects of circadian rhythms. Due to relatively small sample size, the interest will focus more on the estimation and precision of mediating effects rather than significance testing.

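### Does Aim 1's retention proportion need a written definition of who counts as recruited?

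*SAP*

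**What the plan says.** The SAP, Aim 1, sets out a descriptive recruitment sequence. It begins with "the numbers of subjects contacted and screened, the proportion of eligible subjects from those contacted" and continues with "the proportion of those successfully recruited from the pool of eligible subjects, the proportion retained of those recruited". It also plans adherence to outcome reporting by "estimating completion rates of scheduled PSG recordings, core body temperature measures, and self-report forms at both time periods", together with the amount of and reasons for missing data on each outcome. No feasibility threshold, target or test is attached to any of these.

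The protocol gives the order of events. Under Recruitment, item 1, staff "briefly discuss the study and then schedule the visit for recruitment/consent", and the Procedures section uses the same label for the visit: "the investigator/research assistant will schedule the visit for recruitment/consent". Recruitment, item 2, describes the visit as one for consent only. Screening follows consent: "After giving informed consent, candidates will first complete the demographic information and 4 self-administered screening tools", and after the cognitive screen "candidates will then be individually screened/interviewed for the exclusion criteria". Then: "Those who met the study criteria will be scheduled of the study activities". The protocol also says that no personal information is recorded before written consent. Neither document defines recruited or retained.

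**The concern.** Recruited is the numerator of one feasibility proportion and the denominator of the next, so its meaning affects both. The protocol's label for the consent visit joins recruitment to consent, and that visit comes before the eligibility check. The SAP draws the recruited from people already found eligible. Read side by side, the two documents seem to place recruitment on opposite sides of screening.

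Three readings can be listed: everyone who consents; those who consent and are found eligible; and those found eligible who then start the laboratory nights. Each gives a different retention figure from the same people. Retention is a named result in a study that asks for three overnight laboratory visits, so a reader planning a larger trial could take a figure that is too high or too low. An undefined denominator could also be chosen after dropout is known.

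**Working it through.** **1. Which readings does the text allow?** The SAP takes the recruited from the eligible pool. People who consented but failed screening are not in that pool, so the all-consented reading is excluded by the SAP itself. The protocol supports that reading only through the name of a visit, which Recruitment, item 2, does not use. The Procedures section also still calls people candidates after consent and during screening. It calls them participants, enrolled for about three weeks, only after it has described the scheduling of those who met the criteria. That order agrees with the SAP: eligible first, then in the study.

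**2. What separates the two remaining readings?** Let E be the number eligible, S the number eligible who start the laboratory nights, and K the number retained, taken here as completing the post-treatment visit (an assumption, since the SAP does not define it).

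- Eligible reading: recruited/eligible = E/E = 100% always; retention = K/E.
- Started reading: recruited/eligible = S/E; retention = K/S.
- Link: K/E = (K/S) × (S/E).

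**3. Illustration.** The documents give no counts. Assume 50 consented and screened, E = 40, S = 36 and K = 32.

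| Recruited means | Recruited/eligible | Retention | Product |
|---|---|---|---|
| All consented (excluded by the SAP) | 50/40 = 125% | 32/50 = 64.0% | 32/40 = 80% |
| Found eligible | 40/40 = 100% | 32/40 = 80.0% | 32/40 = 80% |
| Eligible and started | 36/40 = 90% | 32/36 = 88.9% | 32/40 = 80% |

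The recruitment proportion of 125% confirms that the first reading cannot be what the SAP means.

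**4. Range of the gap.** The gap between the two live readings is (K/S) × (1 − S/E). Assume 90% of starters are retained:

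- S/E = 60%: 0.90 × 0.60 = 54.0%, a gap of 36.0 points.
- S/E = 95%: 0.90 × 0.95 = 85.5%, a gap of 4.5 points.
- S/E = 100%: no gap.

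The 36-point figure needs 40% of people who had consented and passed screening never to attend a first night. Nothing in the documents suggests this.

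**5. What would the planned output show?** Both proportions are listed together, and (recruited/eligible) × (retained/recruited) = retained/eligible, because the recruited count cancels. The product is therefore the same under every reading. A recruitment proportion below 100% shows that a step after eligibility was used. If it is exactly 100%, retention equals retained/eligible under either reading.

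**6. Earlier stages.** Eligible/contacted mixes willingness to consent with eligibility. The SAP already plans the contacted and screened counts, so the two can be separated, provided screened means the post-consent screen (the only one described). With 500 contacted, also assumed: 50/500 = 10% screened, 40/50 = 80% of those eligible, and 10% × 80% = 8% = 40/500.

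**The case for a change.** The strongest case for a change is that describing feasibility is the whole purpose of Aim 1, and an inferred denominator is not a prespecified one. Even if a step after eligibility is meant, scheduling, the adaptation night, the baseline night and the start of treatment are all candidates, and the baseline night may come up to a week after the adaptation night. Retained is undefined too. A reader who quotes retention alone would not see the choice behind it, and a definition would cost only a few lines.

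Part of this stands: both terms lack a written definition, and the exact step is left to the analyst. But the choice cannot be hidden in the planned output, because moving the step changes recruited/eligible and retention in opposite directions and leaves their product fixed. The planned completion rates for sleep recordings, temperature and questionnaires, with reasons for missing data, help to show where people were lost. Which later step was used, and what counted as retained, are matters of labelling that a results table settles by naming its rows. A definition would make the SAP tidier without altering what a reader can learn.

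**Conclusion.** No change is needed. There is no established conflict between protocol and SAP: the apparent one depends on treating a visit label as a definition, and the SAP's own sentence excludes that reading. What remains is an unwritten definition in a descriptive aim. Analysts can fill it sensibly, since counting the recruited at a step after eligibility is the only choice that makes the recruitment proportion informative.

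The retention figure can shift by the factor started/eligible. On the assumed counts that is 80.0% against 88.9%, about 9 points; it is zero if everyone eligible starts. The true size cannot be taken from the documents. Retained/eligible is unaffected, no decision rule rests on either figure, and the analyses of Aims 2 and 3 do not depend on it. This conclusion assumes that the two proportions are reported together, as the SAP lists them, and that retained is given the same meaning throughout.
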